9.3 Determination of Sample Size

One hundred and eight (108) ITT population subjects (study eyes) per treatment group yields 90% power to reject H_{01} in favor of H_{11} and H_{03} in favor of H_{13} and conclude superiority of AR-15512 (0.003% or 0.0014%) over vehicle in the mean CFB pre-CAE ODS VAS at Day 28, assuming a true difference (AR-15512 minus vehicle) of -8.5, a common standard deviation of 19.0, and a two-sided alpha = 0.05.

Additionally, 108 ITT population subjects (study eyes) per treatment group yields 90% power to reject H_{02} in favor of H_{12} and H_{04} in favor of H_{14} and conclude superiority of AR-15512 (0.003% or 0.0014%) over vehicle in the mean CFB in pre-CAE anesthetized Schirmer score at Day 28 assuming a true difference (AR-15512 minus vehicle) of 1.4 mm, a common standard deviation of 3.15 mm, and a two-sided alpha = 0.05.

Accounting for subject discontinuations, approximately 360 total subjects (120 per treatment arm) will be randomized assuming a dropout rate of 10%.

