- Use of lid heating therapy (i.e., LipiFlow[®], iLUX[®]) or Meibomian gland probing/therapeutic expression within 1 year prior to the Screening visit

Aerie Pharmaceuticals, Inc.

Study Population:

This study is anticipated to enroll approximately 360 subjects with DED so as approximately 324 subjects complete Day 84. The anticipated drop out rate is 10%. To achieve this goal, approximately 1500 subjects may be screened.

Investigational Product, Dose, and Mode of Administration:

BID topical ocular administration of AR-15512 ophthalmic solution 0.0014%, AR-15512 ophthalmic solution 0.003% or AR-15512 vehicle

Duration of Treatment:

Approximately 14 weeks of BID dosing of 1 drop to each of both eyes

Efficacy Assessments:

Primary Assessments:

- Ocular Discomfort Score (ODS) based on Visual Analog Scale (VAS)
- · Anesthetized Schirmer test

Secondary Assessments:

- Ocular Pain Score based on VAS
- SANDE (Symptom Assessment iN Dry Eye) Questionnaire Score
- Eye Dryness Score based on VAS

Safety Assessments:

- Adverse events
- · Hematology, chemistry, and urinalysis
- Best-corrected visual acuity
- Intraocular pressure
- Dilated fundus exam

Statistical Methods:

Sample Size Determination

One hundred and eight (108) ITT population subjects (study eyes) per treatment group yields 90% power to conclude superiority of AR-15512 (0.003% or 0.0014%) over vehicle in the mean change from baseline (CFB) pre-CAE ODS-VAS at Day 28, assuming a true difference (AR-15512 minus vehicle) of -8.5, a common standard deviation of 19.0, and a two-sided alpha = 0.05.

Additionally, 108 ITT population subjects (study eyes) per treatment group yields 90% power to conclude superiority of AR-15512 (0.003% or 0.0014%) over vehicle in the mean CFB in pre-CAE anesthetized Schirmer score at Day 28 assuming a true difference (AR-15512 minus vehicle) of 1.4 mm, a common standard deviation of 3.15 mm, and a two-sided alpha = 0.05.

Accounting for subject discontinuations, approximately 360 total subjects (120 per treatment arm) will be randomized assuming a dropout rate of 10%.

Analyses

AR-15512 Ophthalmic Solution

Clinical Study Protocol: AR-15512-CS201, Amendment 4

Aerie Pharmaceuticals, Inc.

The co-primary efficacy endpoints will be:

- Change from baseline in pre-CAE ODS-VAS at Day 28
- Change from baseline in pre-CAE anesthetized Schirmer score at Day 28

Date of Original Approved Protocol (Rev. 0): 06 August 2020

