4. STUDY POPULATION SELECTION

4.1 Study Population

[figure not shown]
This study is anticipated to enroll approximately 360 subjects with DED as defined below in Sections 4.2 and 4.3 so as approximately 324 subjects complete Day 84. The anticipated dropout rate is 10%. To achieve this goal, approximately 1500 subjects may be screened.

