9.2 Hypotheses

The primary endpoints will be tested in a hierarchical fixed sequence in the following order.

 H_{01} : The difference between study eyes treated with AR-15512 (0.003%) and study eyes treated with vehicle, in the mean change from baseline (CFB) in pre-CAE ODS VAS at Day 28 = 0.

H₁₁: The difference between study eyes treated with AR-15512 (0.003%) and study eyes treated with vehicle, in the mean CFB in pre-CAE ODS VAS at Day $28 \neq 0$.

 H_{02} : The difference between study eyes treated with AR-15512 (0.003%) and study eyes treated with vehicle, in the mean CFB in pre-CAE anesthetized Schirmer score at Day 28 = 0.

 H_{12} : The difference between study eyes treated with AR-15512 (0.003%) and study eyes treated with vehicle, in the mean CFB in pre-CAE anesthetized Schirmer score at Day $28 \neq 0$.

 H_{03} : The difference between study eyes treated with AR-15512 (0.0014%) and study eyes treated with vehicle, in the mean CFB in pre-CAE ODS VAS at Day 28 = 0.

 H_{13} : The difference between study eyes treated with AR-15512 (0.0014%) and study eyes treated with vehicle, in the mean CFB in pre-CAE ODS VAS at Day $28 \neq 0$.

 H_{04} : The difference between study eyes treated with AR-15512 (0.0014%) and study eyes treated with vehicle, in the mean CFB in pre-CAE anesthetized Schirmer score at Day 28 = 0.

 H_{14} : The difference between study eyes treated with AR-15512 (0.0014%) and study eyes treated with vehicle, in the mean CFB in pre-CAE anesthetized Schirmer score at Day $28 \neq 0$.

Hierarchical fixed sequence testing will be employed to maintain the type I error rate. The primary analyses will first test the difference in the mean CFB in pre-CAE ODS VAS between treatments at Day 28, H_{01} . If the test of the difference is statistically significant at the two-sided alpha = 0.05 level in favor of AR-15512 (0.003%), then the trial will be considered a success; AR-15512 (0.003%) will be declared to be superior to vehicle in the mean CFB in pre-CAE ODS VAS at Day 28; and the difference in the mean CFB in pre-CAE anesthetized Schirmer score between treatments at Day 28, H_{02} , will be tested at the two-sided alpha = 0.05 level.

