If in addition to a statistically significant test of the difference in the mean CFB in pre-CAE ODS VAS at Day 28 in favor of AR-15512 (0.003%), the test of the difference in the mean CFB in pre-CAE anesthetized Schirmer score at Day 28 is also statistically significant in favor of AR-15512 (0.003%), then AR-15512 (0.003%) will be declared to be superior to vehicle in both the mean CFB in pre-CAE ODS VAS and the mean CFB in pre-CAE anesthetized Schirmer at Day 28.

If H_{01} and H_{02} are both rejected in favor of AR-15512 (0.003%), then H_{03} and H_{04} will be tested in a similar hierarchical fashion using a two-sided alpha = 0.05.

If H₀₃ and H₀₄ are both rejected in favor of AR-15512 (0.0014%), then the secondary endpoints will be tested between AR-15512 0.003% and vehicle and between AR-15512

0.0014% and vehicle adjusting for multiplicity to maintain an overall two-sided alpha = 0.05 as detailed in the statistical analysis plan.

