2.6 Sample Size Determination

One hundred and eight (108) subjects (study eyes) per treatment group yields 90% power to reject H_{01} in favor of H_{11} and H_{03} in favor of H_{13} and conclude superiority of AR-15512 (0.003% or 0.0014%) over vehicle in the mean change from baseline in pre-CAE Ocular Discomfort score (ODS) Visual Analog Scale (VAS) at Day 28, assuming a true difference (AR-15512 minus vehicle) of -8.5, a common standard deviation (SD) of 19.0, and a two-sided alpha = 0.05.

Additionally, 108 subjects (study eyes) per treatment group yields 90% power to reject H_{02} in favor of H_{12} and H_{04} in favor of H_{14} and conclude superiority of AR-15512 (0.003% or 0.0014%) over vehicle in the mean change from baseline in pre-CAE anesthetized Schirmer score at Day 28 assuming a true difference (AR-15512 minus vehicle) of 1.4 mm, a common SD of 3.15 mm, and a two-sided alpha = 0.05.

Accounting for subject discontinuations, approximately 360 total subjects (120 per treatment arm) will be randomized assuming a dropout rate of 10%.

Version 1.0 Page 9 of 42

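### The 90% power stated for H01 to H04 is the power of each test alone; under the fixed sequence only H01 keeps it, and H03 is at most about 84% at 108 per arm

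*Protocol*

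**What the plan says.** Protocol 9.3 gives two power statements at 108 per arm. For ODS-VAS (true difference -8.5, SD 19.0) the sample "yields 90% power to reject H_{01} in favor of H_{11} and H_{03} in favor of H_{13} and conclude superiority". For anesthetized Schirmer (1.4 mm, SD 3.15 mm) it makes the same 90% claim for H02 and H04. SAP 2.6 repeats both. The synopsis drops the hypothesis labels but says of each endpoint that the sample "yields 90% power to conclude superiority of AR-15512 (0.003% or 0.0014%) over vehicle".

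Protocol 9.2 puts the four hypotheses in a fixed sequence, each tested at two-sided 0.05:

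- H01 (0.003%, ODS-VAS) is tested first. If it is significant "in favor of AR-15512 (0.003%), then the trial will be considered a success", and H02 (0.003%, Schirmer) is tested.
- H03 (0.0014%, ODS-VAS) and H04 (0.0014%, Schirmer) are opened only if H01 and H02 "are both rejected in favor of AR-15512 (0.003%), then". They are then taken in the same hierarchical way.
- If H03 and H04 "are both rejected in favor of AR-15512 (0.0014%), then the secondary endpoints will be tested".

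No readable text says that the 90% is calculated per comparison without the gates. None gives power under the sequence or a correlation between the two endpoints.

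**The concern.** In a fixed sequence, a hypothesis is rejected only if its own test and every earlier test are significant. The power for H02, H03 and H04 is therefore a joint probability, and it is below the power of the single test unless the tests are almost perfectly correlated. Section 9.3 names the hypotheses of 9.2 and speaks of rejecting them and concluding superiority, yet the figure it gives fits only the first.

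A reader planning from 9.3 would take 90% as the chance of establishing both endpoints at 0.003%, or of any claim at 0.0014%. Both are lower. The formal secondary tests wait on H04, so the chance of reaching them is lower still. A missed H03 could also be read as a weak lower dose when the gate accounts for part of the risk.

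**Working it through.** **Inputs from the documents.** Differences 8.5 (SD 19.0) and 1.4 mm (SD 3.15 mm), the same for both doses, two-sided alpha 0.05, n = 108 per arm (Protocol 9.3). Allocation 1:1:1 with one vehicle arm (Protocol 3.1). Test order and gates (Protocol 9.2).

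**Input not in the documents.** The ODS-Schirmer correlation, rho, taken in the direction of benefit. It is assumed to lie between 0 and 0.5, and other values are shown.

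**Step 1: reproduce the stated 90%.** The noncentrality is (difference / SD) × √(n/2), with √(108/2) = 7.348.

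- ODS-VAS: (8.5 / 19.0) × 7.348 = 3.287
- Schirmer: (1.4 / 3.15) × 7.348 = 3.266

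The critical value is t(0.975, 214) = 1.971. The noncentral t gives 90.5% and 90.2%. The stated 90% is reproduced as the power of each test alone. The inflation also holds: 108 / 0.90 = 120.

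**Step 2: apply the gates.** Treat the four test statistics as multivariate normal with the means above.

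- Same endpoint, two doses: correlation 0.5. Each difference has variance 2σ²/n, and the shared vehicle mean contributes covariance σ²/n.
- Two endpoints, same dose: rho.
- Two endpoints, different doses: 0.5 × rho.

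The power at each step is the probability that this statistic and all earlier ones exceed the critical value. For H02 at rho = 0 it is Φ(3.287 − 1.971) × Φ(3.266 − 1.971) = 0.906 × 0.902 = 0.818.

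| n per arm | rho | H01 | H02 | H03 | H04 |
|---|---|---|---|---|---|
| 108 | 0 | 90.6% | 81.8% | 75.9% | 70.4% |
| 108 | 0.5 | 90.6% | 83.9% | 78.2% | 73.9% |
| 108 | 0.9 | 90.6% | 87.4% | 81.5% | 79.3% |
| 120 | 0 | 93.3% | 86.7% | 82.2% | 77.7% |
| 120 | 0.5 | 93.3% | 88.1% | 83.7% | 80.2% |

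The 90.6% for H01 is the normal approximation to the 90.5% of step 1. A subject-level simulation with t-tests (40,000 trials, n = 108, rho = 0) gave 90.5%, 81.5%, 75.8% and 70.1%.

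**Step 3: a ceiling that does not depend on rho.** Rejecting H03 requires at least that H01 and H03 are both significant. These are the same endpoint at two doses, so only the 0.5 correlation enters. P(H01 and H03) = 84.2% at 108 per arm and 88.4% at 120. Likewise H04 cannot exceed P(H02 and H04) = 83.6% at 108 and 87.9% at 120.

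**Step 4: sensitivity to baseline adjustment.** The planned analysis is ANCOVA. If 19.0 and 3.15 are raw SDs of change, and baseline correlates r with change (assumed), the noncentrality is divided by √(1 − r²). For r = 0.3 at 108 per arm and rho 0 to 0.5, H02, H03 and H04 become 86-88%, 82-83% and 77-80%, with an H03 ceiling of 87.9%. For r = 0.5 they become about 93-94%, 91% and 88-89%, with a ceiling of 93.9%.

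**The case against.** The strongest reply is that nothing is miscalculated. Section 9.3 makes separate statements, each with its own difference and SD. It joins the doses with "or", and the gates are set out just before it. Quoting power per comparison is ordinary practice, and trial success rests on H01 alone. This stands as far as it goes: the single-test figures and the sample size are correct. But 9.3 attaches the 90% by name to rejecting gated hypotheses, and no readable text labels it as per comparison.

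A second reply is that the ceiling depends on the SD. The primary analysis adjusts for baseline, and the documents do not say whether the SDs are raw or residual. With a baseline correlation of 0.5 the H03 ceiling would pass 90%. That is a fair limit on the word "cannot". It does not rescue the statement, because the documents give no such correlation. Crediting one would also raise the single-test power above the stated 90%, so that figure would no longer describe the same calculation.

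Third, 108 matches the number expected to complete Day 84: Protocol 4.1 sizes enrolment "so as approximately 324 subjects complete Day 84". The endpoints are at Day 28, so more subjects may contribute. This is also fair, and the rows for 120 per arm show the best case. The H03 ceiling is then 88.4%, still short of 90%.

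Last, the range of 0 to 0.5 for rho is a reviewer's assumption. At -0.3 and 108 per arm the figures would be about 81%, 75% and 69%. H02 returns to about 90% only as rho approaches 1. The ceilings do not use rho.

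**Conclusion.** The concern holds. The 90% in Protocol 9.3, the synopsis and SAP 2.6 is correct as the power of each comparison tested alone and as the power for H01, so power for trial success is not affected. It is not the probability of rejecting H02, H03 or H04 under Protocol 9.2.

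At 108 per arm and rho of 0 to 0.5, the shortfall from 90% is about 6-8 points for H02, 12-14 for H03 and 16-20 for H04. Formal testing of the secondary endpoints is reached with about 70-74% probability. The ranges rest on equal true effects at both doses, the stated SDs used without further gain from baseline adjustment, and the assumed rho. The H03 ceiling needs only the first two and the shared vehicle arm.

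**What to change.** In Protocol 9.3, the synopsis and SAP 2.6, say that 90% is the power of each comparison tested alone, and that it is also the power for H01, the trial success criterion. Add the power under the sequence of 9.2 as a range, and name the assumed endpoint correlation and the number contributing at Day 28. Suggested wording: 'With 108 per arm and an ODS-Schirmer correlation of 0 to 0.5, power under the fixed sequence is about 82-84% for H02, 76-78% for H03 and 70-74% for H04; with 120 per arm, about 87-88%, 82-84% and 78-80%.' If the sponsor has its own estimate of the endpoint correlation, use that instead. State also whether 19.0 and 3.15 are raw or baseline-adjusted SDs, since the figures depend on it.

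The cost is wording in three places and a less favourable stated power for H02 to H04. Sample size, test order and analysis do not change.

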9.4 Analysis Populations

The following analysis population will be considered.

9.4.1 Intent-to-Treat (ITT) Population

The ITT population includes all randomized subjects. The primary efficacy analysis will be performed on the ITT population. Subjects in the ITT population will be analyzed as randomized.

9.4.2 Per Protocol (PP) Population

The PP population includes subjects in the ITT population who do not have significant protocol deviations and who complete the trial through Day 28. Protocol deviations will be assessed prior to database lock and unmasking. The PP population will be analyzed using observed data only for efficacy variables. Subjects in the PP population will be analyzed as treated.

9.4.3 Safety Population

The safety population includes all randomized subjects who have received at least one dose of the investigational product. The safety population will be analyzed for all safety assessments. Subjects in the safety population will be analyzed as treated.

9.5 Demographics and Baseline Characteristics

Subject demographics including age, gender, race, ethnicity, and iris color will be presented using summary statistics (mean, SD, minimum, maximum, and median) or frequency counts and percentages as appropriate.

9.6 Subject Disposition

Subject disposition will be presented in terms of the numbers and percentages of subjects who completed the study and discontinued from the study. Disposition will be summarized by treatment group and for all subjects.

The number of randomized subjects in each of the analysis populations (ITT, PP, and Safety) will be displayed by treatment.

The number and percentage of subjects who prematurely discontinue from the study and the reasons for study discontinuation will be summarized by treatment group for all subjects.

9.7 Efficacy Analysis

9.7.1 Primary Efficacy Endpoint(s)

- Change from baseline in pre-CAE ODS-VAS, at Day 28
- Change from baseline in pre-CAE anesthetized Schirmer score at Day 28

9.7.2 Primary Efficacy Analyses

The primary comparisons in this trial will be between AR-15512 (0.003%) and vehicle with hierarchical analyses between AR-15512 (0.0014%) and vehicle at Day 28 in the ITT population with available data per subject

AR-15512 Ophthalmic Solution

Clinical Study Protocol: AR-15512-CS201, Amendment 4 Aerie Pharmaceuticals, Inc.

The primary efficacy endpoints (e.g., CFB in pre-CAE ODS VAS and CFB pre-CAE anesthetized Schirmer score will be summarized using continuous summary statistics and analyzed separately using an ANCOVA model with terms for baseline value, treatment, and site. In addition, the study site by treatment interaction will be explored in a separate model to evaluate how the treatment effect may differ across study sites.

[figure not shown]
Least squares mean for each treatment group and for the difference between treatment groups will be presented from the model together with two-sided p-values and 95% confidence intervals.

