3. INVESTIGATIONAL PLAN

3.1 Overall Study Design and Plan

This will be a Phase 2b, multicenter, vehicle-controlled, double-masked, randomized study conducted at approximately 15 sites in the United States. All subjects enrolled will have DED. The study will consist of Screening and Baseline visits as well as follow-up visits at Day 14 (Visit 3), 28 (Visit 4) and 84 (Visit 5 / Study Exit). All subjects will be exposed to the CAE at the Screening, Baseline, Day 28 and Day 84 visits. A summary of the overall study design is found in Figure 2.

At the end of the Screening Visit, all qualified subjects will be assigned to administer study vehicle BID to both eyes for 14 days (vehicle run-in period). After the vehicle run-in period, subjects will be re-evaluated for signs and symptoms of DED. Only subjects who requalify, based on inclusion/exclusion criteria, will be enrolled in the study and randomized at a 1:1:1 ratio within each site, to receive AR-15512 0.0014%, AR-15512 0.003% or AR-15512 vehicle to be administered as 1 drop in each eye twice daily for 84 days. Efficacy will be assessed on Visit 3 without use of the CAE and at Visits 4 and 5 pre-, during and post- use of the CAE. Safety assessments will be conducted at each study visit. At the end of Study Visit 5, the subject will exit the study. A summary of all study assessments per visit can be found in Appendix 4 (Schedule of Visits and Procedures).

Figure 2 Study Design

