7.1 Screening Visit (Visit 1; Day -14 (+3*))

- Informed consent
- Inclusion and exclusion criteria
- Demographics
- Medical, ophthalmic, and surgical history
- Prior or concomitant medication review
- Adverse events
- Vital signs (heart rate and blood pressure)
- Urine pregnancy test (WOCBP only)
- Symptom Questionnaire (VAS) (Ocular Discomfort, Eye Dryness and Ocular Pain)
- SANDE Questionnaire (VAS)
- Ora Calibra Ocular Discomfort Scale (ODS)
- Best-corrected visual acuity
- Slit-lamp biomicroscopy
- At least 5 minute rest period
- Anesthetized Schirmer test

• A least 10 minute rest period

- CAE exposure
- Inclusion and exclusion criteria
- Symptom Questionnaire (VAS) (Ocular Discomfort, Eye Dryness and Ocular Pain)
- Ora Calibra Ocular Discomfort Scale (ODS)
- Slit-lamp biomicroscopy

- Review of qualification
- Hematology, chemistry, and urinalysis
- Intraocular pressure
- Dilated fundus exam
- Dispensing of the study treatment
- In office administration of study treatment
- AE review

^{*} Visit 1 should be scheduled between 11 and 14 days before Visit 2. If absolutely necessary, Visit 2 may be delayed up to 7 days (extending the run-in period to a maximum of 21 days).

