9. PLANNED STATISTICAL METHODS

9.1 Statistical Considerations

9.1.1 General Considerations

Quantitative variables will be summarized using number of subjects (n), mean, median, standard deviation, minimum and maximum. Qualitative variables will be summarized using counts and percentages.

All summaries will be presented by treatment group.

For the purpose of summarization, medical history, concurrent therapies, and AEs will be coded to MedDRA and WHO Drug dictionaries, as appropriate.

Baseline measures are defined as the last non-missing measure prior to the initiation of randomized study treatment. If a measure is taken both pre-CAE® and post-CAE®, baseline will be the time point matched value.

Change from baseline (CFB) will be calculated as visit – baseline; treatment comparisons will be calculated as AR-15512 – vehicle; and pre to post CAE comparisons will be calculated as post-CAE minus pre-CAE.

All primary and secondary analyses will be two-sided at a significance level of 0.05.

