3. GENERAL ANALYSIS AND REPORTING CONVENTIONS

This section discusses general policies to be employed in the analysis and reporting of the data from the study. Departures from these general policies may be given in the specific detailed sections of this SAP. When this situation occurs, the rules set forth in the specific section take precedence over the general policies.

All continuous study assessments will be summarized by treatment and time point (as applicable) using descriptive statistics (n, mean, median, SD, minimum, and maximum). All categorical study assessments will be summarized by treatment and time point (as applicable) using frequency counts and percentages.

Hypothesis testing, unless otherwise indicated, will be performed at a two-sided 0.05 significance level. Where applicable, two-sided 95% confidence intervals (CIs) will be reported. All p-values will be displayed to four decimal places, with p-values less than 0.0001 presented as "<0.0001," and p-values greater than 0.9999 presented as ">0.9999."

Differences between AR-15512 and vehicle will be calculated as AR-15512 – vehicle.

Baseline is defined as the last measurement prior to the first dose of investigational product (after randomization). Change from baseline will be calculated as follow-up visit – baseline visit.

The unit of analysis for efficacy will be the study eye.

All study data will be listed by subject, treatment, and time point (as applicable). In the listings, individual subjects will be identified by a combination of site number and subject number, e.g., XXX-YYY, where XXX is the site number and YYY is the subject number.

All data analysis will be performed by Statistics & Data Corporation (SDC) after the study is completed and the database has been locked and released for un-masking. Statistical programming and analyses will be performed using SAS® Version 9.4 or higher. Output will be provided in rich text format (RTF) for tables and portable document format (PDF) for tables, listings, and figures.

Study Eye Criteria

Safety endpoints will be analyzed for both eyes. For efficacy endpoints, the unit of analysis will be the "study eye" (where applicable) as defined by the following:

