8.4 Analysis Methods

8.4.1 Primary Efficacy Analyses

The primary comparisons in this trial will be between AR-15512 (0.003%) and vehicle with hierarchical analyses between AR-15512 (0.0014%) and vehicle at Day 28 in the ITT population

- Population: subjects with DED defined through enrollment criteria
- Endpoint:
 - o Change from baseline in pre-CAE ODS-VAS at Day 28
- Change from baseline in pre-CAE anesthetized Schirmer score at Day 28

Version 1.0 Page 29 of 42

The primary efficacy endpoints (e.g., change from baseline in pre-CAE ODS-VAS and change from baseline pre-CAE anesthetized Schirmer score) will be summarized using continuous summary statistics and analyzed separately using analysis of covariance (ANCOVA) models with terms for baseline value, treatment, and analysis center. In addition, the analysis center by treatment interaction will be explored in a separate model to evaluate how the treatment effect may differ across analysis centers for the ITT population using available data.

Least squares mean for each treatment group and for the difference between treatment groups will be presented from the model together with two-sided p-values and 95% CIs.

Version 1.0 Page 30 of 42

[figure not shown]

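### The primary ANCOVA uses one pre-treatment value although two are collected: adding the Screening value is a free but probably small gain in precision

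*Protocol*

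**What the plan says.** Protocol 9.7.2 analyses the two co-primary endpoints "using an ANCOVA model with terms for baseline value, treatment, and site". SAP 8.4.1 uses "models with terms for baseline value, treatment, and analysis center". The two differ in naming site or analysis center, but each has a single pre-treatment covariate.

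Both documents define that covariate. In Protocol 9.1.1, "Baseline measures are defined as the last non-missing measure prior to the initiation of randomized study treatment". SAP section 3 agrees: "Baseline is defined as the last measurement prior to the first dose of investigational product (after randomization". In practice this is the Day 1 (Visit 2) value.

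The Screening list in Protocol 7.1 also contains "Symptom Questionnaire (VAS) (Ocular Discomfort, Eye Dryness and Ocular Pain" and "Anesthetized Schirmer test", both before CAE exposure. The same items appear in the Visit 2 list (7.2.1) and in the visit schedules of both documents. No readable text uses the Screening values as a covariate, averages them with Day 1, or explains leaving them out.

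**The concern.** Each randomized subject should have two pre-randomization readings of each co-primary measure, separated by the vehicle run-in. A single VAS mark or a single 5-minute strip read to the whole millimetre is a noisy measure of a subject's usual level. Day 1 is also a requalification visit ("Only subjects who requalify, based on inclusion/exclusion criteria, will be enrolled in the study and randomized at a 1:1:1 ratio within each site"), so values that are extreme by chance may be favoured there. If Screening helps to predict Day 28 once Day 1 is known, a model without it has a larger residual variance than the data require.

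What is at stake is precision only. A covariate measured before randomization does not bias the treatment comparison. Any gain would carry through the fixed sequence in Protocol 9.2, where each test depends on the one before and the secondaries follow only if all four primary hypotheses are rejected. The intervals would also be narrower, which is useful in a trial meant to inform later designs (Protocol 3.2).

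**Working it through.** **Inputs from the documents.** Protocol 9.3: for ODS-VAS, "assuming a true difference (AR-15512 minus vehicle) of -8.5, a common standard deviation of 19.0, and a two-sided alpha = 0.05"; for Schirmer, difference 1.4 mm and SD 3.15 mm at the same alpha; 108 per arm for 90% power; 10% dropout; 360 randomized. No correlations between visits are given, so every correlation below is an assumption.

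**Step 1: the plan's own figures.** Two-sample t-test, noncentrality = difference / (SD × √(2/n)), n = 108 per arm.
- ODS-VAS: 8.5 / (19.0 × √(2/108)) = 3.29; power 90.5%.
- Schirmer: 1.4 / (3.15 × √(2/108)) = 3.27; power 90.2%.
- Dropout: 108 / (1 − 0.10) = 120 per arm, 360 in total.

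The stated figures reproduce without a Screening covariate.

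**Step 2: what the covariate does.** The residual variance with Day 1 and Screening, divided by that with Day 1 alone, is 1 − p². Here p is the partial correlation of Screening with Day 28 given Day 1:

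p = (r_S28 − r_B28 × r_SB) / √[(1 − r_B28²)(1 − r_SB²)]

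(S = Screening, B = Day 1, 28 = Day 28.)

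- *Equal correlations ρ.* The ratio becomes (1 + 2ρ)/(1 + ρ)². For ρ = 0.4, 0.5, 0.6 and 0.7 it is 0.918, 0.889, 0.859 and 0.830, a cut of 8%, 11%, 14% and 17%.
- *Partial decay*, for example r_B28 / r_S28 / r_SB = 0.5 / 0.4 / 0.5. p = (0.40 − 0.25)/0.75 = 0.20; the cut is 4%.
- *Full decay*, r_S28 = r_B28 × r_SB (for example 0.25 = 0.5 × 0.5). p = 0; no gain.

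**Step 3: selection at both visits.** Subjects must qualify twice, which narrows the range of both readings and weakens the covariate. The plan screens about 1500 to randomize 360 (24%), but for all reasons together; the share selected on these two measures cannot be read. In simulation (trivariate normal, truncated at the same threshold at Screening and Day 1, about 15% to 60% kept):

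| Assumed correlations (B-28 / S-28 / S-B) | Cut in residual variance |
|---|---|
| 0.4 / 0.4 / 0.4 | 3-5% |
| 0.5 / 0.5 / 0.5 | 5-7% |
| 0.6 / 0.6 / 0.6 | 7-10% |
| 0.7 / 0.7 / 0.7 | 9-13% |
| 0.6 / 0.5 / 0.6 | 2-3% |
| 0.5 / 0.4 / 0.5 | about 2% |
| 0.5 / 0.35 / 0.5 | about 1% |
| 0.5 / 0.25 / 0.5 | 0% |

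**Step 4: power at 108 per arm if 19.0 and 3.15 are residual SDs of the planned model.** Replace SD by SD × √(1 − cut).

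| Cut | ODS-VAS | Schirmer |
|---|---|---|
| 0% | 90.5% | 90.2% |
| 2% | 91.1% | 90.7% |
| 3% | 91.4% | 91.0% |
| 5% | 91.9% | 91.6% |
| 8% | 92.7% | 92.4% |

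**Step 5: power if they are SDs of raw change.** With equal variances, raw change has variance 2σ²(1 − ρ) and the one-baseline ANCOVA has residual variance σ²(1 − ρ²). The residual SD is therefore SD × √((1 + ρ)/2). At ρ = 0.5, 19.0 × √0.75 = 16.45, and ODS-VAS power is already 96.6% under the planned model. A 3-5% cut takes it to 97.0-97.2%.

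**The case against.** The strongest reply is that nothing here is wrong. Both documents specify a standard ANCOVA with a defined baseline, and the planned power holds. Other pre-randomization measures (SANDE, eye dryness and pain VAS, Ora Calibra ODS) are also left out of the model, so asking for one more covariate can look like preference. This stands as to grade: it is an improvement, not a defect. It does not remove the case for the covariate, because an earlier reading of the outcome itself is the natural first candidate and costs almost nothing.

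The second reply concerns size, and it largely stands. Screening is about 42 days before Day 28 and Day 1 is 27. Screening also precedes the vehicle run-in, and artificial tears are allowed until 2 hours before it, whereas anticipated use during the study is an exclusion (Protocol 4.3). Screening may therefore predict Day 28 less well than Day 1 does, and equal correlation is the favourable case.

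Third, part of the text cannot be seen. Some inclusion criteria are missing, so the degree of selection on these measures is unknown. Material around the missing-data and primary-analysis sections of the SAP is also not shown, so imputation or sensitivity models may already use Screening. The terms of the primary model itself are readable.

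**Conclusion.** The point holds as a missed efficiency. The primary model leaves out a second pre-treatment reading of each co-primary measure, and adding it brings no bias and one degree of freedom of cost. The size cannot be fixed from the documents. The cut in residual variance is 0% under full decay, about 1-3% with partial decay and selection, and about 3-13% with equal correlations of 0.4-0.7 and selection. On the residual-SD reading, a 2-3% cut is worth less than one point of ODS-VAS power and a 5-8% cut about one to two points. On the raw-change reading the gain is smaller. The documents do not say which SD is meant.

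Stronger conclusions that a reader might draw are not supported:
- *That the trial is underpowered.* Step 1 shows otherwise.
- *That a gain of 8% to 14% is established.* That needs equal correlations of 0.4 to 0.6 and no selection, whereas subjects qualify at two visits.
- *That a variance cut equals the same percentage of extra subjects.* The equivalent is 1/(1 − cut): a 14% cut corresponds to 1/0.86 = 1.16, about 16% more.
- *That the imputation model omits Screening.* That text is not visible.

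**What to change.** In Protocol 9.7.2 and SAP 8.4.1, add the Screening (Visit 1) pre-CAE value of the same measure as a covariate beside the Day 1 value, treatment and site or analysis center. For Schirmer, take it from the same study eye; the ODS-VAS is rated for both eyes together, so no eye rule is needed. Keep change from Day 1 as the endpoint. State what is done if Day 1 is missing, since the protocol's baseline rule would then fall back on Screening and the two covariates would coincide.

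Use the matching Screening covariate for the continuous secondaries. Include it in the imputation model if it is not already there; that matters because multiple imputation becomes primary once discontinuation reaches 5%, and the plan expects 10% dropout. Specify the change before unmasking and record it in SAP section 12, which currently lists no changes.

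Cost: one degree of freedom and the SAP wording. No new visits, procedures or subjects.
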